2.3 Study Endpoints

The study endpoints (relating to the estimand variables in section 2.2 above) are as follows. Note that the terms 'endpoint' and 'variable' may be used interchangeably throughout this SAP to refer to the measurement of interest:

The primary efficacy endpoint is:

 Change from baseline in Clinician-Completed Congenital DM1 Rating Scale (CDM1-RS) to end of treatment

The key secondary efficacy endpoint is:

 Clinical Global Impression - Improvement Scale (CGI-I) (also referred to as the CGI-C) at end of treatment

The secondary endpoints are:

- Change from baseline in Top 3 Caregiver Concerns VAS score to end of treatment
- Change from baseline in Caregiver Completed Congenital DM1 Rating Scale (CC-CDM1-RS) to end of treatment
- Change from baseline in Clinical Global Impression Severity Scale (CGI-S) to end of treatment
- Change from baseline in Clinician-Completed Congenital DM1 Rating Scale (CDM1-RS) - Independent Central Rater Score to end of treatment
- Clinical Global Impression Improvement Scale (CGI-I) Independent Central Rater Score at end of treatment
- Change from baseline in Clinical Global Impression Severity Scale (CGI-S) Independent Central Rater Score to end of treatment
- Change from baseline in 10-meter walk-run test (preferred speed and fastest speed) to end of treatment

The exploratory endpoints are:

 Change from baseline in DXA Scan measurement of total body lean/muscle mass to end of treatment

- Change from baseline in measurement of lip strength (via lip force meter) to end of treatment
- Change from baseline in Congenital and Childhood Myotonic Dystrophy Health Index (CC-MDHI) Parent Proxy Instrument to end of treatment
- Change from baseline in Autism Behavior Inventory Clinician (ABI-C) to end of treatment
- Change from baseline in standard scores of the Vineland Adaptive
 Behavior Scale to end of treatment
- Change from baseline in quantitative myometric measure of hand grip strength to end of treatment
- Change from baseline in NIH Toolbox Cognition Battery: Dimensional Change Card Sort Test to end of treatment
- Change from baseline in NIH Toolbox Cognition Battery: Picture Sequence Memory Test to end of treatment
- Change from baseline in Peabody Picture Vocabulary Test (PPVT) to end of treatment
- evelssample
- Serial blood pharmacokinetics of tideglusib

[figure not shown]
The Safety endpoints are:

- The incidence of Adverse events (AEs), including serious adverse events (SAEs), between Screening and end of treatment. The incidence will also be assessed during a follow-up period after discontinuation of the study drug for those subjects not participating in the extension study AMO-02-MD-2-004.
- The incidence of abnormal findings in objective assessments (e.g. laboratory values, ECGs, vital signs and bone mineral density) between screening and end of treatment. The incidence of abnormal findings in objective assessments will also be assessed during a follow-up period after discontinuation of the study drug for those subjects not participating in the extension study AMO-02-MD-2-004.

2.4 Study Design

This is a phase 2/3, randomized, double-blind, placebo-controlled, parallel group, superiority study of weight adjusted dose 1000 mg/day tideglusib versus placebo in subjects aged 6 to 16 years with Congenital Myotonic Dystrophy (Congenital DM1) across a treatment period.

Approximately 56 children will be randomized 1:1 into the study in a double-blind manner to either tideglusib or placebo such that each treatment group will have approximately 28 children (assuming a 10-13% drop-out rate) contributing data to the

The overall expected duration of subject participation in AMO-02-MD-2-003 is weeks.

) post end of treatment visit via telephone by a member of the study team.

Visit Structure

The visit structure and scheduled assessments are detailed in Table 1 of the protocol.

3 SAMPLE SIZE

Twenty-five subjects per group will generate 80% power to detect the effect size of 0.82 at the 0.05 two-sided significance level. This sample size will also be sufficient to generate 70% power to detect the effect size of 0.6 at the 0.1 two-sided significance level. Accounting for a 10%-13% drop-out rate, approximately 28 subjects per group will be enrolled.

No data are available on the CDM1-RS instrument. Based on the preliminary data observed in the AMO-02-MD-2-001 study, the assumed effect sizes look reasonable. The effect size assumptions are partially based on the Clinician VAS total score changes from baseline to end of study (6 points on drug vs. 1 point on placebo with the common standard deviation of 5.8). Based on these and other data, and subjects per group will be sufficient to generate 90% and 80% power at the 0.05 two-sided significance level. Based on these calculations, the suggested sample size of 56 subjects total is adequate to detect the treatment effect or at least a consistent trend.

A blinded sample size re-estimation will be performed, per FDA guidance on adaptive designs (Section IV, Adaptive designs based on non-comparative data), once subjects have been enrolled and have completed Visit All study subjects, investigators, site staff and Sponsor's staff and delegates (including the statistical consultant and SQN staff) will remain blinded to treatment assignments.

The blinded sample size re-estimation will be conducted based on the observed standard deviation in the change from baseline in the clinician-completed CDM1-RS at EOT in the ITT population in those subjects who have completed Visit . Summary statistics (mean, median, standard deviation, minimum and maximum) and histograms of the observed values and change from baseline will be provided by visit up to Visit with all subjects being presented under an 'Overall' treatment group. This summary will provide an estimate of the pooled standard deviation for evaluation. Similar summaries will be provided for the clinician-completed CGI-I and the Top 3 Caregiver Concerns VAS score. The blinded external statistical consultant will then conduct the sample size scenarios.

No data on treatment effect and variability based on the CDM1-RS instrument are available; the estimates of mean changes from baseline are not available for placebo, or for the active treatment arm. Three initial scenarios are pre-specified here (treatment effect $\Delta = 5.0, \, \Delta = 3.6, \, \text{and} \, \Delta = 2.1$). However, the clinical relevance of these assumptions is unknown. Additional scenarios will be based on the observed standard deviation and additional assumed treatment differences. Scenarios involving the CGII and/or the Top 3 Caregiver Concerns VAS score may also be assessed. The decisions regarding corresponding sample size increases will be made based on these estimates and other considerations.

Dependent upon the blinded estimate of standard deviation, the sample size may be increased to ensure 80% power for a chosen treatment effect. Any increase in sample size will be limited to 2 times the maximum of the initial sample size. Additional (not pre-specified) scenarios may be requested by the Sponsor after pre-specified scenarios have been reviewed based on various assumptions regarding effect size.

Sample size update due to SSRE

Based on the blinded SSRE, the planned sample size is sufficient to detect the treatment difference between active and control arms based on the primary endpoint with at least 80% power at the 0.05 two-sided significance level. However, the variability of the key secondary endpoint was slightly greater than that originally assumed. Respectively, it was recommended, if operationally feasible, to increase the total sample size to 66 subjects. Further details are in Appendix 2.

As it was not operationally feasible to enroll 66 subjects, 53 subjects were randomized. Sample size calculations based on SSRE results supported this operational decision.

4 RANDOMIZATION

Randomization will occur in a 1:1 manner (e.g. 1000 mg weight adjusted tideglusib: placebo) such that each treatment group will have approximately 28 children and adolescents contributing data to the primary efficacy analysis, stratified by age group,

5 INTERIM ANALYSIS

This study will utilize an independent Data Safety Monitoring Committee (DSMC) with the primary responsibility to monitor both blinded and unblinded information relating to subject safety during the study. A DSMC interim review meeting will be triggered approximately every 3 months following the commencement of the first patient being randomized and dosed with study medication (tideglusib or placebo).

All study staff including the Sponsor will remain blinded until the end of the study.

Full details of the objectives, timing, analyses and the role of the DSMC will be provided in the DSMC charter and DSMC SAP Analysis Plan.

6 ANALYSIS PLAN

6.1 General

Summary statistics for continuous variables will consist of number of non-missing observations (n), mean, standard deviation (SD), minimum, median, maximum, 25th and 75th percentiles unless specified otherwise.

For categorical variables the number and percentage of subjects in each category will be presented, based on the number of subjects in the analysis set, unless otherwise specified.

All statistical tests will be performed using a two-tailed 5% overall significance level, unless otherwise stated. The null hypothesis at all times will be that the treatments are equivalent. All comparisons between the treatments will be reported with 95% confidence intervals for the difference.

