11.4 Statistical Methods for Safety

All safety summaries and analyses will be performed using the SAF.

All AEs will be coded using the MedDRA dictionary and will be summarized by treatment using frequencies and percentages as appropriate.

Protocol No: AMO-02-MD-2-003

Product: Tideglusib AMO Pharma Ltd.

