6.4 Analysis Sets

The following analysis set definitions will be used:

The Enrolled Set includes all subjects for whom informed consent has been provided and assent provided (if applicable), irrespective of whether they received any study treatment.

The **Safety Analysis Set (SAF)** consists of all randomized subjects who received at least one dose of study treatment. Subjects will be presented by treatment actually received. The SAF is the primary population for the analysis of safety data.

The Intent-To-Treat (ITT) set consists of all randomized subjects with at least one post-baseline efficacy assessment. Subjects will be presented in the treatment group they were randomly assigned to. The ITT is the primary population for the analysis of efficacy data.

The Full Analysis Set (FAS) will include all randomised subjects in the SAF for whom any efficacy data were collected post randomisation. Subjects will be included in the analysis set according to the treatment they actually received.

The Pharmacokinetic Analysis Set (PKAS) consists of all subjects in the ITT who receive tideglusib and have at least one evaluable post-dose PK measurement (even if below the limit of quantification). Evaluable PK measurements are defined as those

with dosing information prior to sample collection and sample collection information available. Subjects will be analyzed according to the treatment actually received.

The Per-Protocol Set (PPS) will include all subjects in the FAS who did not have any important protocol violations. Definitions of important protocol violations will be included in the SAP prior to data lock and unblinding. Subjects excluded from the PPS will be determined prior to data unblinding. If no subjects are excluded from the PPS, the PPS will not be required. The PPS will be used for secondary analyses of efficacy data.

All protocol deviations will be assessed and documented on a case-by-case basis prior to the database lock. Important protocol deviations are a subset of protocol deviations that may significantly impact the completeness, accuracy, and/or reliability of the study data or that may significantly affect a subject's rights, safety, or well-being. Important protocol deviations and their impact on the analysis sets for this study are specified in the Protocol Deviations Criteria (PDC) form. Only important protocol deviations will be included in the statistical outputs.

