6.5 Data presentations

The TFLs will present treatment group (i.e. tideglusib or placebo).

TFLs on the PKAS, SAF and FAS analysis sets will be presented according to the treatment actually received (i.e. tideglusib or placebo), regardless of the randomization.

TFLs on the Enrolled, ITT and PPS analysis sets will be presented according to the randomized treatment group.

The data will be summarised in tabular form by treatment group apart from disposition of subjects, protocol deviations and background and demographic data which will be summarised by treatment group and overall subjects.

Only scheduled post-baseline laboratory, vital signs and ECG values will be tabulated, post-baseline repeat/unscheduled assessments will be listed only; all clinically significant values will be noted.

Individual subject assignments to each analysis set will be summarized using the Enrolled set. The primary and key secondary efficacy endpoints will be summarised using the ITT and the PPS. All other secondary endpoints will be summarised using the ITT. PK concentration data will be summarised using the PKAS set and all other data will be summarized using the SAF set. Additionally, run-in data for efficacy and adverse events will be summarised for the RIS set.

Eligibility, completion/withdrawal, consent/assent, analysis set, protocol deviations, demographic and other background listings in section 6.8 and visit dates will be based on the enrolled set, PK listings will be based on the PKAS set, efficacy listings, run-in treatment, study drug dispensing and return, study drug daily dosing and meal intake data, all adverse events and adverse events leading to death will be based on the RIS set and all other listings will be based on the SAF set. Listings based on

the RIS will presented according to the randomized treatment for the efficacy listings and actual treatment received otherwise.

Graphical presentations of the data will also be provided where appropriate. Unless otherwise stated, only data from Visit onwards will be presented graphically.

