6.17.1 Adverse Events

Adverse events (AEs) will be coded using the MedDRA dictionary version applicable at eCRF go-live. The version used will be indicated in the data summaries and listings.

A Treatment-Emergent AE (TEAE) is defined as an AE that started on or after the start of the first dose of double-blind, randomized study treatment. If adverse event dates are incomplete and it is not clear whether the adverse event was treatment-emergent, it will be assumed to be treatment-emergent.

A Non-Treatment Emergent Adverse Event (NTEAE) is defined as an AE that started before the administration of randomized study treatment.

A "double-blind treatment period" TEAE is defined as an AE that started on or after the start of randomized study treatment but before 2 days after randomized treatment was discontinued. A "post treatment period" TEAE is defined as an adverse event that started from 2 days after the randomized study treatment being discontinued.

A treatment related TEAE is defined as a TEAE that is related to the randomized study treatment. If the TEAE has a missing relationship it is assumed to be related to the randomized study treatment for analysis purposes.

The following summaries of the total number of "double-blind treatment period" TEAEs, "post treatment period" TEAEs and all TEAEs (both "double-blind treatment period" and "post treatment period" TEAEs) will be provided at the event and subject levels as indicated:

- TEAEs (number of events and number of subjects).
- Serious TEAEs (number of events and number of subjects).
- Serious randomized study treatment-related TEAEs (number of events and number of subjects).
- TEAEs by severity (mild/moderate/severe) (number of events and number of subjects).
- TEAEs by relationship to randomized study treatment category (unrelated/related) (number of events and number of subjects).
- TEAEs leading to discontinuation from the study (number of subjects only).
- Randomized study treatment-related TEAEs leading to discontinuation from the study (number of subjects only).
- TEAEs leading to death (number of subjects only).

The following summaries of NTEAEs will be provided at the event and subject levels as indicated:

- NTEAEs (events and subjects).
- NTEAEs by severity (mild/moderate/severe) (events and subjects).
- Serious NTEAEs (events and subjects).
- NTEAEs leading to withdrawal (subjects only).
- NTEAEs leading to death (subjects only).

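### Post-treatment TEAE percentages default to the whole Safety Analysis Set, although off-drug follow-up is planned only for children who do not enter the extension study

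*SAP*

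**What the plan says.** **The endpoint and who is followed.** SAP 2.3 (and Protocol 8.1) define the off-drug part of the safety endpoint as incidence "assessed during a follow-up period after discontinuation of the study drug for those subjects not participating in the extension study". The protocol synopsis and Protocol 8.2 and 9.4 give the follow-up period only to these children. Under Protocol 12, the study ends for an extension entrant at the final study assessment, without a follow-up visit, and Protocol 10.5.9 requires AE reporting only up to the final visit. Protocol 7.4 also sends children who stop early to the end-of-treatment visit and then to the follow-up visit.

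**The tables.** SAP 6.17.1 splits TEAEs into a double-blind treatment period and a post-treatment period. The latter is "defined as an adverse event that started from 2 days after the randomized study treatment being discontinued". Both periods, and their total, are summarised overall and by system organ class and preferred term. The overall summary lists "TEAEs (number of events and number of subjects" and similar counts; it names no percentage and no denominator.

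**The percentage and its base.** Protocol 11.4 says that AEs "will be summarized by treatment using frequencies and percentages as appropriate". SAP 6.1 sets the base for categorical data: "based on the number of subjects in the analysis set, unless otherwise specified". SAP 6.5 assigns the set: "all other data will be summarized using the SAF set". Under SAP 6.4 the SAF "consists of all randomized subjects who received at least one dose of study treatment", with no condition on being followed after treatment.

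**The concern.** The endpoint is conditional on not entering the extension, but the default denominator is not. A child who enters AMO-02-MD-2-004 has no planned off-drug follow-up in this study, yet stays in the denominator and is counted as having had no post-treatment event. The printed percentage is therefore not the incidence that SAP 2.3 defines.

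Where the SAP wants another base, it writes one. SAP 6.6 uses the Enrolled Set for screening failures and the Run-In Set for run-in failures, and SAP 6.17.1 uses the Enrolled Set for non-treatment-emergent events. There is no such sentence for post-treatment TEAEs, so silence is hard to read as an implied exception.

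Protocol 10.2.5 says that AE questioning around the post-treatment telephone contacts is meant to bring out dependency, abuse or withdrawal effects. A diluted percentage would make such effects look rarer than they were among the children in whom they could be observed.

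**Working it through.** The documents state no post-treatment incidence, no number followed and no extension uptake, so there is no planned figure to reproduce. The check is how the default percentage relates to the one that the endpoint defines.

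**Inputs**
- Randomised: 53 (SAP 3), an upper bound on the SAF; 53/2 = 26.5, so about 26 per arm.
- Planned dropout d: 10%–13% (SAP 3).
- Share of the SAF entering the extension, e: not stated; treated as unknown.

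**Formula.** Let N be the SAF, F the children followed off drug, and k those with a post-treatment TEAE, all of them among F. The default percentage is k/N and the endpoint's percentage is k/F. With F = N(1 − e), the dilution factor is (k/F)/(k/N) = N/F = 1/(1 − e).

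| Assumed e | Followed of 53 | Factor |
|---|---|---|
| 0% | 53 | 1.0 |
| 25% | 39.8 | 1.33 |
| 50% | 26.5 | 2.0 |
| 67% | 17.7 | 3.0 |
| 75% | 13.2 | 4.0 |
| 80% | 10.6 | 5.0 |
| 87% | 6.9 | 7.7 |
| 90% | 5.3 | 10.0 |

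**Effect of early discontinuers.** If all dropouts attend follow-up and a share u of completers enters the extension, then F/N = d + (1 − d)(1 − u). At u = 1 this is d, so the factor is 1/0.13 = 7.7 or 1/0.10 = 10. If some dropouts are lost, F is smaller and the factor larger. Solving for a factor f gives u = (1 − 1/f)/(1 − d):
- f = 2: 0.5/0.90 = 56% to 0.5/0.87 = 57% of completers.
- f = 3: 0.667/0.90 = 74% to 0.667/0.87 = 77%.

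**Illustration, 26 per arm and two children with an event.** Default: 2/26 = 7.7%. At 50% uptake, 13 are followed: 2/13 = 15.4%. At 75% uptake, 26 × 0.25 = 6.5, so 6 or 7 are followed: 2/6 = 33.3% or 2/7 = 28.6%.

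**Between arms.** With equal uptake, both percentages shrink by the same factor and their ratio is preserved. With unequal uptake it is not. Suppose 30% of followed children have an event in each arm, and uptake is 80% in one and 60% in the other. The default percentages are 0.30 × 0.20 = 6% and 0.30 × 0.40 = 12%, although the rates among followed children are the same.

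**Other safety data.** SAP 6.17.4 tabulates percentages in ECG categories over time, and SAP 6.17.2 gives percentages for categorical laboratory results. The same default would apply to any of these at the follow-up visit. Vital signs (SAP 6.17.3) have no percentage table, and continuous summaries report the number of non-missing observations, so neither is affected.

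**The case against.** **Counts, not percentages.** SAP 6.17.1 lists events and subjects, and counts are not diluted. The table shells are a separate document that is not available here, and they may set another base. This stands as a limit: the whole-SAF percentage is inferred from SAP 6.1 together with Protocol 11.4, and is not written in 6.17.1. But the endpoint is an incidence, and even a bare count cannot be read without the number followed per arm, which no section promises. A base that defines a stated endpoint belongs in the SAP.

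**The size is unknown.** A reader might infer that post-treatment incidence is understated several-fold. The documents do not support that. A factor of 3 needs about two-thirds of the SAF to enter the extension, and no uptake is given. A reader might also infer that the comparison between arms is biased; that needs uptake to differ by arm, on which the documents are silent too.

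**Much is already separated.** The double-blind-period tables stand alone, and every AE is listed with a period flag and relative onset time. SAP 6.17.1 plans no test between arms. This stands: on-treatment safety is not contaminated, and individual post-treatment cases can be found.

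**Who is followed.** Early discontinuers are also directed to follow-up, so those observed are not only completers who decline the extension. Protocol 10.2.5 describes the post-treatment calls without the extension restriction, but the synopsis places them in the follow-up period for non-participants. The first part is right and is built into the calculation and the proposed denominator.

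**Conclusion.** The point holds in mechanism and direction. Read as written, the SAP gives post-treatment-period TEAEs no denominator of their own, and any percentage formed under the 6.1 default is smaller than the incidence defined in SAP 2.3 whenever any child enters the extension.

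The size is conditional: 1.0 with no uptake, 2.0 at 50% of the SAF, and about 7.7 to 10 if all completers enter and only the planned 10–13% dropouts are followed. This assumes that the table shells do not override the default, that no post-treatment event in an extension entrant is recorded in this study, and that early discontinuers attend follow-up as asked.

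A distorted comparison between arms is a possibility, not a finding. Efficacy and double-blind-period safety are untouched. It is worth correcting because a stated safety endpoint would otherwise not be estimated as defined.

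**What to change.** In SAP 6.17.1, state that post-treatment-period TEAE percentages are based on SAF subjects who entered off-drug follow-up, meaning those who did not enter AMO-02-MD-2-004, early discontinuers included. Apply the same base to any categorical ECG or laboratory percentages at the follow-up visit. Print that number for each arm in the column header. Keep the SAF denominator for double-blind-period TEAEs. Footnote the pooled column of all TEAEs to say that children differ in how long they were observed after treatment.

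The cost is one sentence and one programming flag. The August 2024 addendum does not deal with this, so if the tables have already been produced, a supplementary table labelled as added would do. The downside is small denominators and less precise percentages, which reflects how few children may have been observed off drug.
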